#### 10.4 Adverse Events

Throughout the study, all AEs will be evaluated by the PI and noted in the AE section of the source workbook.

AEs will be coded using the Medical Dictionary for Regulatory Activities (MedDRA v21.0 (or most recent version), and reported by system organ class (SOC) and preferred term (PT).

AEs will be classified into the following categories:

- pre-dose AEs: AEs recorded at screening or with a start date and time prior to the first dose of IMP
- treatment-emergent adverse events (TEAEs): AEs that commence during/after the first dose of IMP (ie Period 1) or commence before first dose of IMP (ie a pre-dose AE or existing medical condition) but worsen in intensity during exposure to IMP or NIMP

į

Where the severity of a pre-dose AE intensifies during/after dosing of either IMP or NIMP this will be defined as a new AE and classified as a TEAE.

TEAEs will be assigned to the period in which the AE first occurred. Where the severity of an AE or symptom changes in a subsequent period, this will be defined as a new AE and included under the treatment associated with the subsequent period. AEs that occur during the washout period will be assigned to the treatment the subject received during the period immediately before the washout period.

AEs will be classified as "unrelated", "possibly related", and "related" when considering their relationship to IMP. TEAEs classified as "possibly related" and "related" will be defined as adverse drug reactions (ADRs). An ADR is any AE where a causal relationship with the IMP is at least a reasonable possibility ie "possibly related" or "related". Pre-dose AEs will always have the classification of "unrelated".

AEs will also be classified as "unrelated", "possibly related", and "related" when considering their relationship to NIMP.AEs will be classified as "mild," "moderate" or "severe" when considering their severity.

If the severity or relationship to IMP/NIMP of a TEAE is missing, the severity/relationship will be tabulated as "missing" in the summary tables.

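### SAP 10.4 counts any severity change in a later period as a new TEAE under the later treatment, so a persisting event that fades is counted again in a KD025 + NIMP column

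*SAP*

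**What the plan says.** Four rules in SAP 10.4 bear on an event that spans more than one period.

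- Default: "TEAEs will be assigned to the period in which the AE first occurred".
- Exception: "Where the severity of an AE or symptom changes in a subsequent period, this will be defined as a new AE". The new AE goes under the later period's treatment. The direction of the change is not stated.
- Washout: "AEs that occur during the washout period will be assigned to the treatment the subject received during the period immediately before the washout period".
- Pre-dose events: an event already present before the first IMP dose becomes treatment-emergent only if it gets worse. The TEAE definition says "but worsen in intensity during exposure to IMP or NIMP", and the following paragraph says "Where the severity of a pre-dose AE intensifies during/after dosing of either IMP or NIMP".

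SAP 10.4.1 then sets the counting rules. Subjects are counted once per category within a study period, all events enter the event counts, and percentages use the number of subjects dosed in that period. The severity and relationship summaries count subjects only.

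**The concern.** The section applies a worsening test to one kind of carried-over event and an any-change test to the other, and gives no reason for the difference. Under the any-change test, a moderate headache that starts after KD025 alone and is mild when the next period is under way appears as a moderate TEAE under KD025 alone and as a new mild TEAE under the combination. The subject had one episode, and it was getting better.

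Safety and tolerability is the secondary objective of both parts, and the TEAE tables are laid out by treatment with KD025 alone as one column. A reader will look across those columns, and a rule that can add counts only to the later ones makes that view less reliable.

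**Working it through.** The plan states no figure to reproduce. The check is a reading of the rules, an enumeration of grade changes, and the weight of one subject.

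**1. Does anything limit the exception to worsening?** Protocol 14.1 to 14.3 defines, grades and records AEs but has no rule for assigning them to periods. SAP 10.4.1 and the mock-table footnotes do not mention the direction of a severity change. Nothing limits it.

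**2. Does the new AE qualify as a TEAE?** SAP 10.4 counts "AEs that commence during/after the first dose of IMP (ie Period 1) or commence before first dose of IMP" and then worsen. An AE defined as new in a later period starts after the first IMP dose, so it meets the first limb. Subjects are de-duplicated only within a period, so the one episode stands in two columns.

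**3. Which grade changes trigger the rule?** On the three-grade scale there are 3 × 2 = 6 ordered changes.

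| Change | As written (any change) | Worsening only |
|---|---|---|
| mild to moderate | new AE | new AE |
| mild to severe | new AE | new AE |
| moderate to severe | new AE | new AE |
| moderate to mild | new AE | stays with onset period |
| severe to moderate | new AE | stays with onset period |
| severe to mild | new AE | stays with onset period |

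As written, 6 of 6 changes create a new AE and 3 of those are improvements. Under a worsening rule, 3 of 6 do and none is an improvement. Protocol 8.3 lists a severe AE as a reason for withdrawal from study drugs, so the two improvements from severe should seldom reach a later treatment. That leaves mainly moderate to mild.

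**4. Where can the extra counts fall?** The order is fixed. Part 1 runs KD025 alone, + itraconazole, + rabeprazole, + rifampicin; Part 2 runs KD025 alone, + omeprazole. A subsequent period is therefore always a KD025 + NIMP period. In Part 1 the event may come from Period 1 or from an earlier test period (Period 2 into 3, for example).

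**5. What is one case worth?** If the subject has no other TEAE in that category and period, the column percentage rises by 100/N, where N is the number dosed in that period. At the planned enrolment:

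- Part 1: 100/40 = 2.5 points
- Part 2: 100/38 = 2.6 points

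The actual N may differ. At 34 subjects the figure is 100/34 = 2.9; at the permitted maximum of 44 in Part 1 it is 100/44 = 2.3, and at 42 in Part 2 it is 100/42 = 2.4. If the subject already has a TEAE in that category and period, the subject count does not move. In either case the TEAE event count rises by one.

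**6. When does a subsequent period start?** SAP Table 1 puts the first itraconazole dose and the first omeprazole dose on Day 3 of Period 1 (unless the washout is extended), under the next treatment. An event that drops a grade on or just after that day could be read as Period 1, as washout (earlier treatment), or as the subsequent period (new TEAE under the combination). The SAP does not say which.

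**The case against.** The case for leaving the rule alone is that few events will meet it. The event must be moderate, persist past the washout, and drop a grade in a later period. Minimum washouts are 2, 8 and 4 days in Part 1 and 2 days in Part 2. The washout rule may keep many fading events with the earlier treatment, a subject with an AE leaves the unit only with authorisation (Protocol 10.3.3), and eligibility is checked again at admission (10.2). The tables are descriptive, with no safety test or decision rule, and every TEAE is listed individually. All of this stands and limits the size. It does not make the count right when the rule is triggered.

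A reader might also infer more than the documents support:

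- *That a recovery is reported as a drug reaction, or blamed on the NIMP.* The rule assigns a period and a treatment column. Relationship to IMP and to NIMP is classified separately, and an event judged unrelated stays unrelated. ADR counts rise only if the event is judged possibly related or related to IMP.
- *That resolving events in general are moved.* Full resolution is not a severity grade and creates no new AE; an unchanged event stays with its first period.
- *That the shift is always from reference to test.* In Part 1 it can also run from one test treatment to a later one. What holds is that the extra count never lands in the KD025-alone column.
- *That each case adds an event to the relationship tables.* Those tables count subjects only. A carried-over Period 1 event can bring a subject into the NIMP-relationship table, which omits Period 1, but under whatever relationship was assigned.

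**Conclusion.** The inconsistency is in the text and the double count follows from it: SAP 10.4 asks for worsening in pre-dose events and for any change in events carried between periods. An event that persists into a later period at a lower grade is counted again as a TEAE, always in a KD025 + NIMP column.

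The effect per case is about 2.5 points in a Part 1 column or 2.6 in the Part 2 omeprazole column, plus one event. This assumes planned enrolment as the number dosed and no other TEAE for that subject in that category and period. How many cases will arise cannot be derived from the documents; the washout rule and the severe-AE withdrawal rule suggest few. The effect is confined to the descriptive safety tables for the secondary objective, and the primary PK conclusions are unaffected. It is worth correcting because a stated rule yields a wrong count and the correction is cheap.

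**What to change.** In SAP 10.4:

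1. Change the subsequent-period rule so that only worsening creates a new AE under the later treatment, in line with the pre-dose rule.
2. State that an event that improves or is unchanged stays with its period of onset in the summary tables. Grade changes can still be shown in the listings.
3. State when each period starts for AE assignment, how this fits the washout rule, and how an event is assigned when itraconazole or omeprazole is first given on Day 3 of Period 1.

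The first item is one word and the second one sentence, with a matching change to the AE derivation program. The third needs a short decision, because changing the word alone leaves the period boundary open. Protocol 15.4 has the analysis plan signed off before database lock, so the change belongs there; made later, it should be documented as a change to the planned analysis. No data collection changes, and worsening events are still counted under the later treatment.

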#### 10.4.1 Summary Tables for Adverse Events

All pre-dose AEs (as defined in Section 10.4) will be excluded from the summary tables but will be listed for all subjects.

Descriptive statistical methods will be used to summarise the TEAE data.

The number and percentage of subjects reporting each TEAE will be summarised for both SOC and PT. For summaries by SOC and PT, with the exception of TEAEs by severity and relationship to IMP, the number of subjects and the number of events will be summarised. For summaries by severity and relationship only the number of subjects will be summarised.

For counts of subjects experiencing events the following will apply:

- a subject experiencing TEAEs in more than one body system, within a study period, will be counted once in the total number of subjects with TEAEs in that study period;
- a subject with more than 1 TEAE in the same SOC, within a study period, counts only once at the SOC level;
- a subject with more than 1 TEAE in the same PT, within a study period, counts only once at the PT level.
For event counts, all events are included.

When it is necessary to calculate percentages, the denominator will be the total number of subjects in the safety dataset for that period (ie number of subjects dosed in each period, shown in TABLE 14.1.1.1

and the numerator will be the total number of subjects reporting a TEAE within the relevant category.

Summaries presented for SOC and PT will be presented in descending order of frequency overall ie most frequently reported SOC in the study and then by most frequently reported PT in the study within each SOC.

### 10.4.1.1 Overall Summary of Adverse Events

The following will be summarised for the safety population by treatment:

- number and percentage of subjects reporting at least 1 TEAE
- number and percentage of subjects reporting at least 1 ADR
- number and percentage of subjects reporting at least 1 TEAE leading to subject withdrawal
- number and percentage of subjects reporting at least 1 severe TEAE
- number and percentage of subjects reporting at least 1 serious TEAE
- number and percentage of subjects reporting at least 1 TEAE leading to death
- total number of TEAEs
- total number of ADRs
- total number of TEAEs leading to subject withdrawal
- total number of severe TEAEs
- total number of serious TEAEs
- total number of TEAEs leading to death

### 10.4.1.2 Summary of Treatment-Emergent Adverse Events by System Organ Class and Preferred Term

All subjects reporting TEAEs will be summarised by treatment. Counts will be given for number of subjects and number of events. Subjects experiencing more than 1 TEAE within a period will be counted only once for number of subjects but will be counted more than once for number of events.

Additionally, subjects reporting TEAEs will be summarised for SOC and PT by treatment. Counts will be given for number of subjects and number of events. For programming purposes, counts of number of subjects will be by maximum severity ie subjects experiencing more than 1 episode of a TEAE within a period will be counted only once within each SOC and PT using the most severe episode.

### 10.4.1.3 Summary of Treatment-Emergent Adverse Events by Severity

All subjects reporting TEAEs will be summarised by severity (mild, moderate or severe) and treatment. Counts will be given for number of subjects, not number of events. Counts will be given by maximum severity (ie subjects experiencing more than 1 TEAE within a period will be counted only once using the most severe episode).

Additionally, subjects reporting TEAEs will be summarised for SOC and PT by maximum severity (ie mild, moderate or severe) and treatment. Counts will be given for total number of subjects, not for events. Counts by maximum severity will be given (ie subjects experiencing more than 1 TEAE within a period will be counted only once within each SOC and PT using the most severe episode).

# 10.4.1.4 Summary of Treatment-Emergent Adverse Events by Relationship to IMP

All subjects reporting TEAEs will be summarised by relationship to IMP (ie unrelated, possibly related and related) and treatment. Counts will be given for number of subjects, not number of events. Counts will be given by the closest relationship to IMP (ie subjects experiencing more than 1 TEAE within a period will be counted only once using the most closely related event).

Additionally, subjects reporting TEAEs will be summarised for SOC and PT by closest relationship to IMP (ie unrelated, possibly related or related) and treatment. Counts will be given for total number of subjects, not for events. Counts by closest relationship will be given (ie subjects experiencing more than 1 TEAE within a period will be counted only once within each SOC and PT using the most closely related event).

# 10.4.1.5 Summary of Treatment-Emergent Adverse Events by Relationship to NIMP

All subjects reporting TEAEs will be summarised by relationship to NIMP (ie unrelated, possibly related and related) and treatment (Periods 2 to 4 of Part 1 and Period 2 of Part 2 only). Counts will be given for number of subjects, not number of events. Counts will be given by the closest relationship to NIMP (ie subjects experiencing more than 1 TEAE within a period will be counted only once using the most closely related event).

Additionally, subjects reporting TEAEs will be summarised for SOC and PT by closest relationship to NIMP (ie unrelated, possibly related or related) and treatment. Counts will be given for total number of subjects, not for events. Counts by closest relationship will be given (ie subjects experiencing more than 1 TEAE within a period will be counted only once within each SOC and PT using the most closely related event).

### 10.4.1.6 Summary of Adverse Drug Reactions (ADRs)

All subjects reporting ADRs will be summarised by treatment. Counts will be given for number of subjects and number of events. Subjects experiencing more than 1 ADR within a period will be counted only once for number of subjects but will be counted more than once for number of events.

Additionally, subjects reporting ADRs will be summarised for SOC and PT by treatment. Counts will be given for number of subjects and number of events. For programming purposes counts of number of subjects will be by maximum severity ie subjects experiencing more than 1 episode of a TEAE within a period will be counted only once within each SOC and PT using the most severe episode.

### 10.4.1.7 Summary of Serious Adverse Events

All subjects reporting serious adverse events (SAEs) will be summarised by treatment. Counts will be given for number of subjects and number of events. Subjects experiencing more than 1 SAE within a period will be counted only once for number of subjects but will be counted more than once for number of events.

Additionally, subjects reporting SAEs will be summarised for SOC and PT by treatment. Counts will be given for number of subjects and number of events. For programming purposes counts of number of subjects will be by maximum severity ie subjects experiencing more than 1 episode of a SAE within a period will be counted only once within each SOC and PT using the most severe episode.

### 10.4.2 Listings for Adverse Events

All pre-dose AEs (as defined in Section 10.4) will be listed including SOC and PT.

A separate data listing of all TEAEs will be provided including the SOC and PT. In addition, a listing of all SAEs will be provided.

### 10.5 Laboratory Evaluations

The details of sample collection for laboratory safety analysis are described in the study protocol.

Where a value is provided by the safety laboratory as either above or below the limit of detection this will be set to the limit of detection itself for summary purposes. No imputations will be made in the individual listings.

### 10.5.1 Summary Tables for Laboratory Evaluations

Haematology and clinical chemistry data will be summarised (mean, SD, median, minimum, maximum and n) for each laboratory parameter at each time point, including changes from baseline at the 48 h (Day 3) post-baseline time point by treatment. For the purposes of laboratory evaluations baseline is defined as follows:

- for Part 1, Periods 1, 2 and 4: Day -1, Admission for each relevant period
- for Part 1, Period 3: Day -3, Outpatient Visit
- for Part 2, Periods 1 and 2: Day 1, pre-dose for each relevant period

Shift tables from baseline to the 48 h post-baseline time point (with respect to the number and percentage of subjects with values below, within or above the reference range) will be presented by treatment. Percentages will be based on the number of subjects with measurements at baseline and the 48 h post-baseline time point.

### 10.5.2 Listings for Laboratory Evaluations

The sample collection data (eg collection times) for laboratory analysis and urinalysis data will be listed.

All individual subject data, for planned haematology, clinical chemistry, and urinalysis data including derivations such as change from baseline will be listed. If applicable, data from unscheduled laboratory tests will also be listed and flagged with a # to indicate it will not be used in the summary statistics. In these listings, individual data will be flagged

with an "H" or an "L" for values that are higher or lower than their reference ranges, respectively.

Separate listings of all haematology, clinical chemistry and urinalysis values outside their reference ranges by subject will also be provided. References ranges will be supplied by the safety laboratory for haematology and clinical chemistry and per the study workbook for urinalysis (ie a positive or negative result) with the exception of the following reference ranges for urinalysis:

- pH 5.0-9.0 (as per the limits of the current dipstick range)
- Specific gravity 1.000 to 1.030

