6.4 Risks and Benefits

6.4.1 Potential Risks associated with KD025

KD025 has generally been well tolerated across the clinical studies conducted. No drug-related AEs have resulted in fatal outcomes. The most common AEs associated with KD025 administration are liver-related, specifically increased ALT and AST levels. Subjects will receive single doses of KD025 in this study and will be closely monitored throughout the study for any changes in liver enzymes, and no subject with a history or presence of hepatic disease or ALT/AST values > the upper limit of normal (ULN) will be enrolled in the study (see Section 9.3).

Other commonly reported events include rash, pruritus, upper respiratory infection, joint aches and swelling, headache, fatigue, back pain, leg weakness, diarrhoea, nausea, vomiting, upper abdominal pain, increase in white blood cell count, catheter site infection, dizziness, and flatulence.

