8.3 Subject Withdrawal

If a subject wishes to leave the study at any time, they will be permitted to do so. Every reasonable effort will be made by Quotient Sciences to complete a final assessment/discharge procedures. Quotient Sciences will advise the sponsor of the withdrawal of any subject from the study.

Early withdrawal is defined as the date of the decision to withdraw the subject from the study. Subject completion is defined as the date of the last procedure conducted or last contact (ie, phone call) for that subject.

If a subject requests to leave the clinical unit earlier than the planned discharge time eg due to unforeseen personal circumstances, but aims to return to the unit to complete the study, this will be documented as a subject self-discharge and a protocol deviation. The subject must complete the planned assessments/discharge procedures before discharge from the clinic and will return for the next study period/assessments, as planned.

Subjects will be withdrawn from the study drugs for the following reasons:

- Experiencing a serious or severe AE including but not limited to:
 - corrected QT (QTc) interval of >500 msec or increase in QTc interval of >60 msec from baseline (confirmed following a repeat ECG [mean of triplicate assessments, as applicable])
 - ALT concentration >3 × the upper limit of the reference range
- Termination of the study
- Upon the subject's request (withdrawal of consent)
- Significant deviation from the protocol
- Concurrent illness or requirement for prohibited medication
- At the discretion of the investigator/sponsor

For the purpose of withdrawal criteria in Parts 1 and 2, baseline will be considered as the Period 1 admission/pre-dose measurement; for QTc withdrawal criteria, baseline will be considered as the mean value of the triplicate pre-dose Day 1 (Period 1) ECG measurement.

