### 10.7.2 Listings for ECG Data

All ECG data (ie single and individual and mean of triplicate readings) including derivations such as change from baseline (mean of triplicate Day 1, pre-dose values for each period [ie morning dose for Part 2]) will be listed.

All ECG data will be flagged with an "H" or an "L" for values that are higher or lower than their reference ranges, respectively. If applicable, data from unscheduled ECG assessments will also be listed and flagged with a # to indicate it will not be used in the summary statistics.

In addition, subjects with increase in QTcF interval from baseline (30-60 msec) and with 'substantial increases' (>60 msec) will be flagged with 'l' and 'SI', respectively.

A separate listing of all ECG parameters outside their reference range by subject will also be provided.

The reference ranges (from the study day workbook for all parameters, except QT Interval, which is from Quotient SOP "The Interpretation of the Electrocardiogram, Vital Signs and Clinical Laboratory Data During Phase I / II Clinical Trials") and defined in Table 8 will be used.

Parameter	Split	Lower limit	Upper limit
Ventricular Pote (HP)	18-45 years	40 bpm	90 bpm
	>45 years	50 bpm	90 bpm
PR Interval	NA	120 msec	220 msec
QRS Duration	ŅA	0 msec	120 msec
QT Interval	NA	0 msec	500 msec
QRS Axis	NA	-30°	100°
QTcB/QTcF Interval	NA	0 msec	450 msec
Rhythm	NA	Sinus r Sinus bradycardia Sinus ar	hythm, ı (rate dependent), rhythmia

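### The safety tables leave gaps between QTc classes, count no ALT >3x ULN, and measure QTc increases from a different baseline than the withdrawal rule

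*SAP*

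**What the plan says.** **Withdrawal rule.** Protocol 8.3 gives two numerical triggers as examples of a serious or severe AE. One is "ALT concentration >3 × the upper limit of the reference range". The other is "corrected QT (QTc) interval of >500 msec or increase in QTc interval of >60 msec from baseline (confirmed following a repeat ECG"; the bracket goes on to mention the mean of triplicate readings where applicable. For QTc, the rule's baseline is the Period 1 Day 1 pre-dose triplicate mean, whatever period the subject is in.

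**Laboratory tables.** SAP 10.5.1 summarises observed values, with their maximum, at each time point, "including changes from baseline at the 48 h (Day 3) post-baseline time point by treatment". Shift tables use the same single time point and count subjects "with values below, within or above the reference range". Under SAP 10.5.2, "data from unscheduled laboratory tests will also be listed and flagged with a # to indicate it will not be used in the summary statistics".

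**ECG tables.** SAP 10.7.1 averages the triplicates and then counts QTcB and QTcF in Table 7. The absolute classes are ≤450, 451-480, 481-500 and >500 msec. The increase classes are <30, 30-60 and >60 msec. The baseline is each period's own Day 1 pre-dose triplicate mean. Under SAP 10.7.2, "data from unscheduled ECG assessments will also be listed and flagged with a # to indicate it will not be used in the summary statistics".

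**Known risk.** Protocol 6.4.1 states: "The most common AEs associated with KD025 administration are liver-related, specifically increased ALT and AST levels".

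**The concern.** Safety and tolerability are the secondary objective of both parts. Liver enzymes are the main known KD025 risk, and Part 1 adds itraconazole and rifampicin, for which Protocol 6.4.2 describes hepatotoxicity and hepatitis respectively. A reader of the report will want to know how many subjects crossed the limits that the protocol itself set, and under which treatment.

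The planned laboratory and ECG tables do not answer that directly:

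- No laboratory table uses a multiple of the upper limit.
- Repeat samples and repeat ECGs taken because a value was abnormal (Protocol 14.5.6 and 14.7) are unscheduled, so they stay out of the summaries.
- The QTc increase table and the QTc withdrawal rule start from different baselines after Period 1.
- Some QTc means have no class to go into, so the counts at a time point need not add up to the number measured.

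**Working it through.** The plan states no figure to reproduce here. The check sets the table definitions against the values they must hold.

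**1. Table 7, absolute classes.** Assume each QTc reading is a whole number of milliseconds. A mean of three then has fractional part 0, 1/3 or 2/3. If one reading is missing, SAP 10.7.1 averages the other two, giving 0 or 1/2. All possible means of one, two or three readings from 300 to 600 msec were compared with the four classes:

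- Between 450 and 451: 450.33, 450.5 and 450.67 fit no class.
- Between 480 and 481: 480.33, 480.5 and 480.67 fit no class.
- Every value above 500 falls in the >500 class.

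**2. Table 7, increase classes.** A difference between a mean of three and a mean of two moves in steps of 1/6 msec. All steps from -100 up to +150 msec were compared with <30, 30-60 and >60. None is unclassified, and every increase above 60 falls in the top class.

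**3. Can rounding close the gaps?** SAP 13.1 has a general rounding convention but does not apply it before classification. If it did, 450.33 would become 450 and find a class. However, 500.33 would become 500 and drop into 481-500, and an increase of 60.33 would become 60 and drop into 30-60. Rounding would create the loss that the present classes avoid.

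**4. ALT.** In the shift table, ALT of 1.1x ULN and of 3.1x ULN at 48 h both fall in the above-range class. The number above 3x ULN cannot be recovered from that class. The maximum at a time point can show that at least one scheduled value exceeded 3x ULN, but not how many subjects did.

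The Part 1 flow chart (Protocol Appendix 2) also schedules laboratory tests on Day -5 of Period 4, during rifampicin dosing. The Period 4 baseline is Day -1, so Day -5 precedes it and lies outside both change and shift. A subject withdrawn on the Day -5 result would have no Period 4 sample at 48 h. Because shift percentages need both a baseline and a 48 h value, that subject would not appear in the Period 4 shift table.

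**5. QTc confirmation.** Under Protocol 14.7, Part 1 readings are triplicate only at pre-dose and 4 h. By the flow chart, 2 h and 12 h are single. A single scheduled reading above 500 msec is counted in Table 7, and it stays counted whether the unscheduled repeat confirms or refutes it.

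**6. QTc baseline.** Let B1 be the Period 1 baseline, Bk the current period's baseline and Y the post-dose value. The withdrawal rule uses Y - B1 and the SAP table uses Y - Bk, so the two differ by Bk - B1. With illustrative values:

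| B1 | Bk | Y | Rule: Y - B1 | Table: Y - Bk | Table class |
|---|---|---|---|---|---|
| 400 | 420 | 465 | +65 | +45 | 30-60 |
| 420 | 400 | 465 | +45 | +65 | >60 |

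In the first row a subject exceeds the rule's limit but is not in the >60 class. In the second row it is the other way round. This can arise in Periods 2 to 4 of Part 1 and in Period 2 of Part 2. In Period 1 the two baselines are the same.

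**The case against.** The strongest reply is that the withdrawals are tabulated elsewhere. Protocol 8.3 treats both triggers as serious or severe AEs, and clinically significant laboratory or ECG abnormalities must be reported as AEs whether scheduled or not. SAP 10.4.1.1 tabulates, by treatment, TEAEs leading to withdrawal, severe TEAEs and serious TEAEs. SAP 7.2 tabulates reasons for discontinuation. Out-of-range values have their own listings, QTcF increases above 60 msec are flagged there, and with at most 44 and 42 subjects dosed the listings can be read by eye. Protocol 5.3.2 adds that earlier liver events generally came after 16 to 36 days of KD025, whereas here KD025 is given on four or two separate days. All of this stands, and it limits the size of the point. It does not supply a count by ALT or QTc threshold, nor show which QTc readings were confirmed.

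Keeping unscheduled values out of by-visit means is also ordinary practice and should stay. A reader might infer that such values are barred from every summary. SAP 13.1 allows them to replace a missing baseline.

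A reader might also infer that the Table 7 gaps hide withdrawal-level QTc events, or that the tables cannot count such events at all. The documents do not support either reading. The gaps lie at 450-451 and 480-481 msec, well below the limits, and a scheduled triggering reading is already counted by time point and overall. Dropping the repeat tends to over-count. Under-counting of values above 500 msec arises only where the triggering reading was itself unscheduled.

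Finally, follow-up laboratory tests are not firm ground for the argument. The flow charts in Protocol Appendices 2 and 3 schedule them, but Protocol 10.3.6 describes follow-up as a telephone contact.

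**Conclusion.** The point holds in three limited parts.

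1. Table 7 is misspecified for replicate means: six possible values fit no class. This is a definite error, though the documents do not show how often it would occur, and it affects no value above the >500 or >60 msec limits.
2. No laboratory summary counts ALT >3x ULN. The count must be taken from listings or inferred from the AE and disposition tables.
3. The QTc outlier table does not separate confirmed from unconfirmed readings. After Period 1 its count of increases above 60 msec can differ from the withdrawals in either direction, by an amount set by the shift in baseline.

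The consequence is weaker reporting of a secondary objective. No data are lost and the pharmacokinetic conclusions are untouched. The result rests on QTc being recorded in whole milliseconds and on classification being applied to unrounded means. The baseline figures are illustrations, not estimates.

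**What to change.** - Rewrite the absolute classes in Table 7 as ≤450, >450-480, >480-500 and >500 msec, applied to unrounded values.
- Keep by-visit descriptive statistics on scheduled data.
- Add one worst-post-dose table per treatment that includes unscheduled results: ALT and AST >1x and >3x ULN, QTcF >500 msec, and QTcF increase >60 msec. Count post-dose from the first dose of any study drug for that treatment, so that the Period 4 Day -5 sample is included.
- In that table, show the mean of the confirmatory repeat beside the triggering QTcF reading, and give the increase from both the period baseline and the Period 1 baseline.
- Reconcile the QTc baseline in Protocol 8.3 with the one in SAP 10.7.1, or state in the SAP that they differ on purpose. Protocol 8.3 also does not name the QT correction, so the SAP should say which one its table uses for the comparison.
- Include follow-up laboratory results only once Protocol 10.3.6 and the flow charts in Appendices 2 and 3 have been reconciled.

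The cost is one or two extra programmed tables and an edit to Table 7. No new data or visits are needed.
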